10.2.5 SAEs (Including Deaths) and Adverse Events Leading to Study Drug Discontinuation

SAEs (including deaths) and AEs leading to study drug discontinuation will be summarized by SOC and PT and in listing format.

10.2.6 Adverse Events of Special Interest

Treatment-emergent AESIs will be summarized by SOC and PT and will be based on standardized or company MedDRA queries (SMQs or CMQs), or based on adjudication results, as specified in [Appendix G](#).

Treatment-emergent AESIs will be summarized by SOC and PT and listing format. Additionally, the event rate per 100 patient years of exposure will be provided for provided by SOC and PT for each AESI in the AE overview summary.

10.3 Analysis of Laboratory Data

Data collected from central and local laboratories, including additional laboratory testing due to an SAE, will be used in the analyses. Baseline values collected for SAE-related laboratory assessments on or before the first dose of study drug will be excluded. Data collected more than 70 days after the last dose of study drug of the analysis period (See Section [10.2.1](#)) for the corresponding analysis populations will be excluded.

The clinical laboratory tests defined in the protocol (e.g., hematology and clinical chemistry) will be summarized.

Analysis of Quantitative Laboratory Parameters

Each laboratory variable will be summarized at all time points (starting at baseline) with the number of observations, mean, standard deviation, median, minimum and maximum

for non-missing observations. The change from Baseline at each applicable post-baseline visit will be summarized for selected laboratory variables, with the number of observations, baseline mean, and visit mean. The mean, standard error, and 95% CI will be presented for the change from Baseline for each treatment group.

For each period, treatment group differences for the changes from baseline will be analyzed using a one-way Analysis of Variance (ANOVA) model with treatment as a fixed factor and 95% CI for treatment difference will be presented for selected laboratory parameters.

Shift Table Analyses

Changes in laboratory parameters will be tabulated using shift tables categorized as low, normal, or high based on the normal ranges of the laboratory used for each sample. A shift table summarizes shifts from baseline to minimum and maximum values (based on normal range) will be created. A similar shift table will be provided to summarize shifts from baseline to the final post-baseline value.

Potentially Clinically Significant Laboratory Values

The criteria for potentially clinically significant laboratory values will be determined by CTCAE criteria of Grade 3, Grade 4 and \geq Grade 3, with a grade worsening compared to baseline. Toxicity grading scale is based on National Cancer Institute Common Toxicity Criteria (NCI CTC) AE version 5.0. The number and percentage of subjects meeting the criteria for potentially clinically significant laboratory values will be summarized by treatment group. Listings of subject-level laboratory data will be provided for subjects meeting the criteria.

Assessment of Liver Elevations

The liver-specific laboratory tests include the serum glutamic pyruvic transaminase (SGPT/ALT), serum glutamic-oxaloacetic transaminase (SGOT/AST), alkaline phosphatase (ALP), and total bilirubin (TBL). The frequencies and percentages of

subjects with post baseline liver specific function test values that meet the following criteria of potential clinical interest will be summarized by treatment group:

- $ALT > 3 \times ULN$
- $ALT > 5 \times ULN$
- $ALT > 10 \times ULN$
- $ALT > 20 \times ULN$
- $AST > 3 \times ULN$
- $AST > 5 \times ULN$
- $AST > 10 \times ULN$
- $AST > 20 \times ULN$
- $TBL > 1.5 \times ULN$
- $TBL > 2 \times ULN$
- $ALP > 1.5 \times ULN$
- $ALT \text{ and/or } AST > 3 \times ULN \text{ and } TBL > 1.5 \times ULN$
- $ALT \text{ and/or } AST > 3 \times ULN \text{ and } TBL > 2 \times ULN$
- $ALT > 3 \times ULN \text{ and } TBL > 1.5 \times ULN$
- $ALT > 3 \times ULN \text{ and } TBL > 2 \times ULN,$

where ULN is the upper normal limit. The maximum ratio relative to the ULN will be used to determine if subjects meet any of the criteria listed above.

A listing of subjects, defined as those meeting the following criteria will also be provided:

- $ALT \text{ and/or } AST > 3 \times ULN \text{ and/or } ALP > 1.5 \times ULN \text{ and } TBL > 1.5 \times ULN$

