7.10 Sample Size Determination

Approximately 265 subjects will be randomized into 4 ABBV-154 treatment groups or placebo in a 1:1:1:1:1 ratio at Baseline of the Induction Period. There will be a cap of approximately 30% the total enrolled of subjects who had prior use of adalimumab treatment.

A total of 265 subjects (53 subjects per group) will provide more than 90% power to detect a 26% difference in endoscopic response rates at Week 12 of the Induction Period between an ABBV-154 group and the placebo group (assuming the response rate in the placebo group is 11%) using a Chi-square test at α level of 0.1 (two-sided).

Under the response rate assumptions for ABBV-154 and placebo in the Induction Period, it is expected that at least 40 subjects per group will be available for the analysis of endoscopic response at Week 40 in the Maintenance Period. This sample size (40 subjects per group) will provide more than 80% power to detect a 26% difference between ABBV-154 and placebo (assuming the response rate in the placebo group at Week 40 of the Maintenance Period is 11%) using a Chi-square test at α level of 0.1 (two-sided).

The total sample size (planned as 265 subjects) for the Induction Period may be adjusted to ensure at least 40 subjects per group for the analysis in the Maintenance Period.

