4.0 Analysis Populations

The following population sets will be used for the analyses.

ITT Populations

ITT population: The ITT Population includes all subjects who were randomized and received at least 1 dose of study drug.

ITT1 population: The subset of the ITT Population who were randomized and received at least 1 dose of study drug in the Induction Period. The ITT1 Population is the primary analysis population for efficacy analyses of the Induction Period.

ITT2 population: The subset of the ITT population who were randomized and received at least one dose of study drug in the Re-Induction Period. The ITT2 Population is the analysis population for efficacy analyses of the Re-Induction Period.

ITT3 population: The subset of the ITT population who received ABBV-154 for 12 weeks before entering the Maintenance Period (including subjects were randomized to ABBV-154 dose groups in the Induction Period and entered the Maintenance Period from the Induction Period OR were randomized to the placebo group in the Induction Period and entered the Maintenance Period from the Re-Induction Period) AND were randomized and received at least one dose of study drug in the Maintenance Period. The ITT3 Population is the primary analysis population for efficacy analyses of the Maintenance Period.

ITT3-RN population: The subset of the ITT population who were enrolled and received at least one dose of study drug in the randomized portion of the Maintenance Period.

ITT3-NRN population: The subset of the ITT population who were enrolled and received at least one dose of study drug in the non-randomized portion of the Maintenance Period.

ITT3-RES population: The subset of the ITT population who received at least one dose of ABBV-154 rescue therapy in the Maintenance Period.

The ITT Populations (including ITT1, ITT2, ITT3, ITT3-RN, ITT3-NRN populations) will be analyzed as randomized (i.e., according to the randomized/assigned treatment assignment).

Safety Populations

The safety population for the Induction Period (denoted by **SA1**) includes all subjects who received at least one dose of the study drug in the Induction Period.

The safety population for the Re-Induction Period (denoted by **SA2**) includes all subjects who received at least one dose of the study drug in the Re-Induction Period.

The safety population for the Maintenance Period (denoted by **SA3**) includes all subjects who received at least one dose of the study drug in the Maintenance Period.

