9.2.2 Continuous Endpoints

For continuous efficacy endpoints where Mixed-Effect Model Repeat Measurement (MMRM) analysis or Analysis of Covariance (ANCOVA) is performed, missing data will be handled using the following approaches.

- MMRM: The repeat measurement analysis will be conducted using a mixed model including observed measurements at all post-baseline visits for the respective analysis period up to the end of the analysis period. The mixed model includes the categorical fixed effects of treatment, visit and treatment-by-visit interaction, stratification factors at randomization, and the continuous fixed covariates of baseline measurement. An unstructured variance covariance matrix will be used. If the model cannot converge, an appropriate variance-covariance structure matrix (e.g., autoregressive or compound symmetry) will be used. Parameter estimation is based on the method of restrictive maximum likelihood (REML). MMRM will be the primary approach in the analysis of continuous variables with repeated measurements.
- ANCOVA: For continuous efficacy variables that are collected at only one post-baseline visit (such as SES-CD), ANCOVA will be used. The model includes the categorical fixed effects of treatment, stratification factors at randomization, and the continuous fixed covariates of baseline and measurement.

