10.0 Safety Analyses

10.1 General Considerations

Safety analyses will be performed on the safety population for the Induction Period (SA1), the Re-Induction Period (SA2), the Maintenance Period (SA3) and SA-RES, SA-ALL154 population as defined in Section 4.0. In addition, safety summaries will be

performed on the safety analysis set for combined data from different periods (SA-IN2, SA-INMN, SA-IN2MN).

The standard safety analyses will include reporting of adverse events (AEs), adverse events of special interest (AESIs), laboratory, and vital signs measurements. Frequency tables and exposure adjusted event rate per 100 patient-years tables of subjects with treatment-emergent adverse events (TEAEs) by system organ class (SOC) and by preferred term (PT) as in the Medical Dictionary for Regulatory Activities (MedDRA) dictionary will be provided by treatment group. All continuous laboratory parameters and vital signs variables at each visit will also be summarized by treatment group. Frequency tables of subjects meeting criteria for potentially clinically important vital sign values and for potentially clinically important laboratory values will be provided by treatment group.

For safety analyses (such as analyses of laboratory and vital signs measurements) in the Induction Period, the baseline value is defined as the last available measurement before study drug administration for all subjects (including subjects who received placebo). For all other safety analyses, the baseline value is defined as the last available measurement before first administration of ABBV-154 for all subjects.

For the safety analysis, subjects are assigned to a treatment group based on the treatment actually received, regardless of the treatment randomized.

Missing safety data will not be imputed.

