10.4 Analysis of Vital Signs

Vital sign measurements of systolic and diastolic blood pressure, pulse rate, body weight, respiratory rate and body temperature will be summarized. Data collected more than 70

days after the last dose of study drug of the analysis period (See Section 10.2.1) for the corresponding analysis populations will not be included.

Each vital sign variable will be summarized at all time points (starting with Baseline) with the number of observations, mean and standard deviation, median, minimum and maximum for non-missing observations. Change from Baseline at each applicable post-baseline visit will be summarized for each vital sign variable, with the number of observations, Baseline mean, and visit mean. The mean, standard error, and 95% CI will be presented for the change from Baseline for each treatment group.

For each period, treatment group differences for changes from Baseline will be analyzed using a one-way Analysis of Variance (ANOVA) with treatment as a fixed factor and 95% CI for treatment difference will be presented for each vital sign variable.

Vital sign variables will be evaluated based on potentially clinically important (PCI) criteria (See ABBV-154 PSSAP). For each vital sign PCI criterion, the number and percentage of subjects who have a vital sign value meeting the criteria will be summarized. Listings will be provided to summarize subject-level vital sign data for subjects meeting PCI criteria.

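### In the randomized comparisons, laboratory and vital-sign changes should be analysed by ANCOVA with baseline as covariate, not by one-way ANOVA on the change score

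*SAP*

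**What the plan says.** For each period, SAP 10.3 states that "treatment group differences for the changes from baseline will be analyzed" with a "one-way Analysis of Variance (ANOVA) model with treatment as a fixed factor", and it gives a 95% CI for the treatment difference. This covers a selected set of laboratory parameters that the section does not name. SAP 10.4 does the same for every vital sign, by "one-way Analysis of Variance (ANOVA) with treatment as a fixed factor".

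SAP 10.1 supplies the baseline. In the Induction Period, "the baseline value is defined as the last available measurement before study drug administration for all subjects", placebo subjects included. For all other safety analyses, "the baseline value is defined as the last available measurement before first administration of ABBV-154 for all subjects".

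The efficacy part of the SAP treats baseline differently. Section 9.2.2 puts the baseline measurement into the repeated-measures model as a covariate and adds: "For continuous efficacy variables that are collected at only one post-baseline visit (such as SES-CD), ANCOVA will be used". That ANCOVA also carries baseline. The SAP gives no reason for using a different model for the safety variables.

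**The concern.** Analysing change with treatment as the only term fixes the regression slope on baseline at 1. Unless the true slope is 1, the comparison carries avoidable noise, and a chance difference in baseline between arms passes partly into the estimated difference in change.

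This matters here because safety in comparison with placebo is part of the primary objective (Protocol 3.1). Protocol 2.2 names hypertension and diabetes among the known glucocorticoid effects and commits to monitoring blood pressure and glucose. Induction randomization is stratified by glucocorticoid use, SES-CD and adalimumab response (Protocol 5.8), so neither design nor model controls an imbalance in, say, blood pressure. The planned intervals are wider than they need to be for detecting modest mean shifts.

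**Working it through.** **The plan's own figures.** The documents give no variance, correlation or precision figure for any laboratory or vital-sign comparison. Their power statement concerns the primary endpoint: "A total of 265 subjects (53 subjects per group) will provide more than 90% power to detect a 26% difference". With 53 per group, 11% against 37%, two-sided alpha 0.1 and a chi-square test, power is 94.1%. The Maintenance statement (40 per group, more than 80%) gives 87.1%. Both hold, and neither is affected by this point.

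**Inputs.** Five groups of 53, 265 in total (Protocol 7.10). The correlation rho between baseline and follow-up, and the ratio lambda = SD at follow-up / SD at baseline, are assumptions.

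**Equal standard deviations (SD = s, lambda = 1).**
- Change score: variance per subject 2s²(1 − rho).
- ANCOVA: residual variance s²(1 − rho²).
- Ratio (1 + rho)/2; reduction (1 − rho)/2; interval width factor √((1 + rho)/2).

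| rho (assumed) | Variance cut | Interval narrower by |
|---|---|---|
| 0.2 | 40% | 22.5% |
| 0.4 | 30% | 16.3% |
| 0.5 | 25% | 13.4% |
| 0.7 | 15% | 7.8% |
| 0.8 | 10% | 5.1% |
| 0.9 | 5% | 2.5% |
| 0.95 | 2.5% | 1.3% |

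A simulation with five groups of 53 and 6,000 runs gave cuts of 30.7%, 14.0% and 4.1% at rho 0.4, 0.7 and 0.9, against 30%, 15% and 5% by formula.

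**Unequal standard deviations.** The reduction is (1 − lambda·rho)² / (1 + lambda² − 2·lambda·rho). The numerator is a square, so the reduction is never negative.
- lambda = 1.25: (1 − 0.5)²/1.5625 = 16% at rho 0.4; (1 − 0.875)²/0.8125 = 2% at rho 0.7.
- lambda = 0.8: (1 − 0.32)²/1.00 = 46% at rho 0.4; (1 − 0.56)²/0.52 = 37% at rho 0.7.

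**Cost of the covariate.** One degree of freedom. With 265 subjects in one model, the error degrees of freedom are 259 and the variance inflation is about 1 + 1/258, or 0.4%. Net of this, the 30% and 15% become 29.7% and 14.7%. For a two-group fit with 106 subjects the inflation is about 1 + 1/102, or 1%.

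**Chance imbalance.** The standard error of a baseline difference between two arms of 53 is s√(2/53) = 0.19s. Given a baseline difference d and equal standard deviations, the unadjusted comparison of change is shifted by −(1 − rho)d. At rho 0.5 (assumed), an imbalance of two standard errors (0.39s) shifts it by about 0.19s. ANCOVA removes this shift.

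**Where the comparison is not randomized.** SA3 "includes all subjects who received at least one dose of the study drug in the Maintenance Period", analysed as treated. It therefore takes in placebo-induction responders, who are assigned 80 mg without re-randomization (Protocol 4.1). Their first ABBV-154 dose comes at the start of Maintenance, so under SAP 10.1 their safety baseline falls about 12 weeks later than that of subjects given ABBV-154 in Induction. Baselines can then differ systematically between groups, and ANOVA on change and ANCOVA can estimate different quantities.

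**The case against.** The strongest reply is that nothing here is wrong. The change-score estimate is unbiased under randomization, its interval already carries the baseline noise, and efficacy models do not bind safety summaries. Overall type I error control is not planned (SAP 12.0). Safety is also judged by shift tables, Grade 3 or higher values with worsening, vital-sign criteria and adjudicated glucocorticoid events, and baseline means are shown beside visit means, so an imbalance would be visible.

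Most of this stands, and it limits the importance of the point. It does not make the choice of model a matter of taste: in a randomized comparison ANCOVA cannot lose more than about a degree of freedom, whatever rho is.

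It is also fair to say that wider intervals and chance imbalance are one effect, not two. With equal standard deviations the variance removed is 2s²(1 − rho) − s²(1 − rho²) = s²(1 − rho)², which is exactly the imbalance component. They should not be counted as separate harms.

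A reader might infer four stronger things that the documents do not support:
- That baseline is ignored. It is subtracted; only the covariate is missing.
- That a gain of 15% to 30% is established. It needs rho of 0.7 to 0.4 and equal standard deviations, and the documents supply neither.
- That ANCOVA is a free gain in every period. In Maintenance as SA3 defines it, the change is not purely one of precision.
- That glucocorticoid effects on lipids or weight would be missed. The protocol's lists of glucocorticoid effects (2.1, 2.2) include neither, and SAP 10.3 does not say which laboratory parameters are modelled.

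**Conclusion.** The point holds as a minor improvement for the randomized comparisons: Induction, Re-Induction and the randomized portion of Maintenance. The direction of the gain does not depend on rho. Its size does: with equal standard deviations, a variance cut of 30% to 15% for an assumed rho of 0.4 to 0.7, and 10% or less from 0.8 upwards, so little for very stable parameters. If follow-up values are more variable than baseline values (lambda 1.25), the cut over rho 0.4 to 0.7 is only 16% to 2%; if less variable (lambda 0.8), it is 46% to 37%. The planned analysis is valid in these comparisons, only less precise than it could be. No sample size, primary endpoint or secondary endpoint depends on it.

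**What to change.** In SAP 10.3 and 10.4, for the randomized comparisons in each period, replace the one-way ANOVA with ANCOVA: treatment as factor, the parameter's own baseline value (SAP 10.1) as covariate, and a 95% CI for the adjusted difference. Leave the descriptive summaries as they are.

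For Maintenance, state that the adjusted comparison is confined to re-randomized subjects, and that placebo-induction responders assigned 80 mg are excluded from it or described separately. For 230 mg against placebo, it would be consistent to apply the exclusion of Induction Group 1 responders that SAP 9.1 already makes for efficacy.

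The cost is SAP wording, one model term and one degree of freedom. No new data, visits or subjects are needed. A change score already requires both values, so the same subjects contribute.

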10.4 Analysis of Vital Signs

Vital sign measurements of systolic and diastolic blood pressure, pulse rate, body weight, respiratory rate and body temperature will be summarized. Data collected more than 70

days after the last dose of study drug of the analysis period (See Section 10.2.1) for the corresponding analysis populations will not be included.

Each vital sign variable will be summarized at all time points (starting with Baseline) with the number of observations, mean and standard deviation, median, minimum and maximum for non-missing observations. Change from Baseline at each applicable post-baseline visit will be summarized for each vital sign variable, with the number of observations, Baseline mean, and visit mean. The mean, standard error, and 95% CI will be presented for the change from Baseline for each treatment group.

For each period, treatment group differences for changes from Baseline will be analyzed using a one-way Analysis of Variance (ANOVA) with treatment as a fixed factor and 95% CI for treatment difference will be presented for each vital sign variable.

Vital sign variables will be evaluated based on potentially clinically important (PCI) criteria (See ABBV-154 PSSAP). For each vital sign PCI criterion, the number and percentage of subjects who have a vital sign value meeting the criteria will be summarized. Listings will be provided to summarize subject-level vital sign data for subjects meeting PCI criteria.

11.0 Interim Analyses

An interim analysis will be performed when approximately 66% of the subjects (35 subjects per group) have reached Week 12 of the Induction Period or have prematurely discontinued the study to inform the development of future studies. The interim analysis will be conducted by an independent AbbVie team outside of the blinded M20-371 study team. The interim analysis result will be reviewed by Internal Executive Review Committee (IERC) from AbbVie.

IERC members are not involved in this study but have the scientific and technical expertise and experiences for making decisions based on the interim analysis results. The interim analysis result will not be reviewed by external Data Monitoring Committee (DMC).

A separate interim unblinding plan will be developed to describe the detailed interim analysis plan, including the interim unblinding team, decision rules, execution logistics, and data chain of custody to protect the integrity of the clinical study. The interim analysis plan will not be documented in the DMC charter.

An additional interim analysis in the Maintenance Period might be performed to inform the development of future studies. The results from this analysis will not impact the conduct of the current study.

